Several met-analyses of risk factors for postpartum depression have been conducted (Beck 2001, O'Hara & Swain, 1996; Robertson et al., 2004). The findings from these meta-analyses suggest that the following risk factors have the strongest association with developing postpartum depression: a) history of depression, b) elevated depressive symptoms during pregnancy, c) poor social support, d) stressful life events, e) poor marital relationship, and f) low socioeconomic status. Our previous research with HV programs suggest that nearly all HV clients exhibit one of these risk factors, with most clients exhibiting multiple risk factors. This is due to the fact that eligibility criteria for inclusion

in HV programs mirror these risk factors for postpartum depression—particularly, low SES, low social support, and stressful life events. As such, we will not limit our inclusion criteria for this study to only individuals exhibiting elevated depressive symptoms, as this would potentially exclude women at risk for postpartum depression. Moreover, there is the potential for underreporting of depressive symptoms on screening instruments, which would lead to under enrollment of women at risk for developing major depression.

Women with high-risk medical and pregnancy conditions will be excluded since this may preclude women from regularly attending intervention sessions. We will not exclude women based on race/ethnicity or based on demographic characteristics other than the ability to speak English or Spanish.

Clinicians: 18 HV programs will receive the MB intervention delivered by clinicians. We will train approximately 18 clinicians to deliver MB. Although there will be variability in the expertise among clinicians, all clinicians will have a minimum of a Master's Degree and at least five years' experience working with children < 5 and their families. The clinicians will live and work in the three different regions of Illinois where this study will be conducted: Chicago, downstate Illinois, and western Illinois as well as adjacent states who are participating in the study

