month prior to implementation, we will train home visitors and mental health professionals on MB. We will stagger implementation in two waves so that only half the sites are implementing at once. This will allow our Intervention Coordinator to focus her efforts on ensuring attendance at intervention groups and fidelity to intervention protocols. Study recruitment and implementation of all prenatal MB sessions will be completed by the 4th quarter of Year 2. This recruitment schedule will allow us to complete all postnatal MB sessions and follow-up data collection by the middle of Year 3, allowing study investigators to analyze data and prepare to disseminate study findings to both academic and community stakeholders.

Participant Screening: Participants will initially be screened for eligibility criteria by their home visiting program sites. Upon permission from the potential study participant, program sites will fill out a referral form, which will include the potential study participants name and contact information, and send it to the research team. Once the program sites refer potential study participants, a member of the study team will call the participant using the “Phone Script for Referrals” to screen the potential study participant for eligibility criteria and move forward with the consent process either via telephone or REDCap survey link.

Participant Outcomes Surveys: Participant outcomes will be collected at four time points—baseline, post-intervention, 12 weeks postpartum, and 24 weeks postpartum. Participants will receive \$20 remuneration at the baseline, 12-week and 24-week assessments. The MMS and EPDS will be administered to all clients during their baseline surveys. This information will be used for data analytics but not as an exclusion criteria. Data will only be collected from study participants who have consented to participate in the study.

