The post-intervention assessment consists of one depressive symptom measure, so no remuneration will be provided. Baseline and follow-up data will be collected and managed using REDCap (Research Electronic Data Capture), a secure web-based application designed to support data capture for research studies, hosted and supported by Northwestern’s Clinical and Translational Science Institute. Once research staff enters participant contact information, REDCap will generate emails or texts containing web-based survey links at scheduled time points. Baseline data will be collected within 2-3 weeks of establishing client eligibility and participation agreement. Women who do not complete the web-based baseline assessment in this timeframe will be contacted by phone by the Research Coordinator to complete the assessment either by phone or online, ensuring that baseline data are collected prior to the first MB group. Informed consent will be obtained prior to administering the baseline assessment. If a study participant decides that they do not want to consent to participate in this study, no data will be collected from this participant. For the post-intervention, 12-week postpartum, and 24-week postpartum assessments, study participants who do not complete web-based assessments within one week of the web link being sent to them will be contacted by the research team to complete the assessments by phone.

Table 4 describes this study’s outcome indicators, measures, and data collection timelines.

Outcome Indicator	Measure	Baseline	Post-Intervention	12 weeks postpartum	24 weeks postpartum
Depressive Symptoms	Edinburgh Postpartum Depression Scale	X			
Current & Lifetime Major Depressive Episode	Maternal Mood Screener (MMS)	X		X	X

DEPRESSION					
Depressive Symptoms*	Quick Inventory of Depressive	X	X	X	X
Symptomatology					
PROXIMAL OUTCOMES					
Behavioral Activation	Behavioral Activation	X		X	X
Pleasant Activities	Pleasant Activities Schedule	X		X	X
Mood Regulation	Negative Mood Regulation Scale	X		X	X
Social Support	MOS Social Support Survey	X		X	X
Decentering	Experiences Questionnaire	X		X	X
Relationship w/Partner	Dyadic Adjustment Scale	X		X	X
Responsive and Reactive Parenting	Parental Cognitions and Conduct toward the Infant Scale			X	X
Subjective Well-Being	Flourishing Scale	X		X	X
Perceived Stress	4-item Perceived Stress Scale	X		X	X
PRENATAL HEALTH BEHAVIORS					
DEMOGRAPHICS					
INTERVENTION SKILL USE					
INVOLVEMENT IN PRENATAL SERVICES					

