We will administer the Maternal Mood Screener (MMS) (Le & Muñoz, 1998) to assess for history of MDD and current MDD. The MMS is a self-report checklist that assesses MDD using DSM-V criteria. Previous research supports the MMS as a valid instrument for MDD screening (Vasquez et al., 2008). Women meeting MDD criteria who are not currently in treatment will be referred to the supervisor at their HV agency.

During any of the research assessments, if the participant endorses current thoughts of harming herself or others, the following protocol should be followed, and documented on an Incident Report.

Maternal Mood Screener (MMS), Question 9d

→ *In the past 2 weeks, subject endorses she has attempted suicide in the past two weeks*

The Quick Inventory of Depressive Symptomatology (QIDS), Question 12

→ *In the past week, subject selects answer #3 (I thought of suicide or death several times a day in some detail, or I made specific plans for suicide or actually tried to take my life)*

The Edinburgh Postnatal Depression Scale (EPDS), Question 10

→ *In the past week, subject endorses thoughts of harming herself quite often*

When assessments are completed over the phone or online during regular business hours the following protocol will be completed within 24 hours.

Within 24 hours of the study participant's completion of their assessments a member of the Research team will call the study participant and will let the participant know that he/she will be contacting their home visiting program to let them know about the difficulties they are having with thoughts about death/suicide/hurting yourself/others, so they can reach out and offer support. The research team member will ask the study participant the following questions:

- "Are you thinking about killing yourself?"
- "Have you ever tried to hurt yourself before?"
- "Have you thought of ways that you might hurt yourself?"
- "Do you have pills/weapons in the house?"
- "Do you think you might try to hurt yourself today?"
 - If her response is Yes, then call 911 and stay on the phone with her until help arrives

All individuals that complete the above surveys will receive the following resources immediately upon answering the above answer choices on the noted assessments

- ✓ Home Visiting Program Office phone number
- ✓ National Suicide Prevention Hotline (24/7)
 - [name] ([name])
 - <http://www.suicidepreventionlifeline.org/> (online chat available 24/7: "Lifeline Chat")

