 - ii. **At least one** of the problems must be: symptom 1 (feeling depressed) or symptom 2 (losing interest or pleasure), **and**
 - iii. The participant indicates '**yes**' to the question: *Did these problems interfere with your life or activities a lot?*
2. Behavioral activation scale score (BA)
3. Social support (due to the highly skewed nature of this outcome, we dichotomized it into ≥ 4 versus <4).
4. Mood regulation
5. Decentering
6. Mental health service utilization (i.e., an indicator for whether participants are enrolled in therapy with a counselor and/or currently taking antidepressants). This outcome may be explored in greater detail in a separate paper; however, we plan to examine the difference between arms controlling for baseline mental health service utilization.

Tertiary Outcomes (the following will be explored in a separate paper from the primary results)

1. Pleasant activities
2. Perceived stress
3. Parental cognitions and conduct toward the infant scale
4. Dyadic adjustment scale
5. Flourishing scale
6. Prenatal health behaviors

The outcomes above are tied to validated scales with specific scoring requirements. The scoring instructions will be followed and analyses will proceed on the final, scored variables. In addition, we plan to summarize '**dosage**' of intervention in the active intervention arms as the number of sessions attended (out of six possible). We will also summarize the number of participants that were '**compliant**', which is defined as attending **at least four of the six sessions**.

Demographics and Baseline Assessments

The following are specific demographic/baseline assessments of interest for analyses. Primary analyses will adjust for these covariates as we anticipate they will influence outcome. We plan to report both adjusted and unadjusted intervention effect estimates:

1. Race/ethnicity (at the participant level): minority vs. not belonging to a minority category.
2. Whether participant is a first-time mother (i.e., current number of children = 0 at baseline).
3. Currently at risk for depressive episode (i.e., those NOT meeting criteria for MDE at baseline).

4. Primary language of intervention receipt (for MH and HV arms) or primary language in which the participant completed assessments (for control arm).
5. Education: at least some college vs. less than college.

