Analyses will proceed at the participant level. Primary analyses for QIDS-SR16 score at 24 weeks postpartum will involve all the participants in the study contributing data at this time point. Primary analyses will involve a linear mixed model for continuous outcome with independent fixed effect variables of baseline QIDS-SR16, study arm (three-level factor), and the baseline covariates listed above. We will report both covariate-adjusted and unadjusted estimates for intervention effect. Secondary analysis will be performed on those participants considered at risk at baseline (i.e., excluding the participants who do not meet the criteria for MDE as defined above). We plan to account for clustering effects via inclusion of a random site effect, which will allow for distinction of between and within-site variance. We will also explore inclusion of a random 'facilitator' effect as it is possible participants exposed to the same facilitator may have correlated responses. Intra-cluster correlation coefficients will be estimated via variance components estimates.

Intervention effect will first be evaluated via the adjusted Wald type III test for significant study arm effect at the 5% level of significance. If arm is significant at the 5% level, analyses evaluating the **superiority (Aim #1)** of HV-led intervention vs. control will proceed with Tukey's correction for multiple pairwise hypothesis tests. Assuming the Tukey-adjusted p-value for this comparison falls below the 5% level of significance in favor of the HV-led arm, **non-inferiority (Aim #2)** will further be assessed (using Tukey's correction) via pairwise comparison of adjusted 24-month QIDS in HV-led vs. MH-led arms. Figure 1 below depicts the margin and zone of non-inferiority for this comparison.

[figure not shown]

Figure 1. Margin of Non-inferiority (NI)

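### Lifetime history of major depression is collected at baseline but left out of the adjusted models without a stated reason; adding it would be a small, nearly free gain

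*SAP*

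**What the plan says.** **What is collected.** Protocol section 15.0 says the MMS is given "to assess for history of MDD and current MDD". Table 4 in Protocol section 4.0 lists it as "Current & Lifetime Major Depressive Episode", at baseline and at 12 and 24 weeks postpartum. Of the baseline MMS and EPDS, section 4.0 says: "This information will be used for data analytics but not as an exclusion criteria".

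**What the protocol says about prognosis.** Section 3.0 reports from meta-analyses that "the following risk factors have the strongest association with developing postpartum depression" and opens the list with "a) history of depression, b) elevated depressive symptoms during pregnancy".

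**What the model contains.** SAP, Demographics and Baseline Assessments, gives the reason for its covariates: "Primary analyses will adjust for these covariates as we anticipate they will influence outcome". They are minority status, first-time motherhood, not meeting MDE criteria at baseline, language, education, and two indicators for counseling and depression medication at baseline. SAP, Statistical Methods, specifies a linear mixed model with "independent fixed effect variables of baseline QIDS-SR16, study arm (three-level factor), and the baseline covariates listed above", plus a random site effect. SAP, Secondary Outcomes, defines MDE on the past two weeks.

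Lifetime history is absent from the covariates, the other variables to be summarized, the Aim 3 effect modifiers and the baseline table shell. No reason is given.

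**The concern.** The SAP chooses covariates because they are expected to predict outcome. Lifetime MDE fits that reason on the protocol's own account and is already in the database schedule, yet only the current-episode part of the MMS is used.

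The covariates that are included do not fully replace it. Current MDE looks back two weeks, and the QIDS item that the protocol reproduces looks back one week. Counseling and medication are recorded as current use, and Protocol section 2.0 says that low-income women with depressive symptoms, home visiting clients included, do not access community treatment. A woman with past episodes who is well and untreated at baseline can therefore look the same to the model as one who has never been ill.

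What is at stake is some precision, and adjustment for chance imbalance in a prognostic factor. There are only six control sites, and allocation was constrained only on percent non-White clients, client volume and population density.

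**Working it through.** The documents give no figure for this covariate choice. The SAP's non-inferiority power serves as the starting point.

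**1. Reproducing the SAP.** Inputs from Power and Sample Size Considerations: SD 6, margin 2, ICC 0.01, 16 v 16 sites, 23 analysed per site, significance level 1.7% (two-sided reproduces the table).
- Design effect = 1 + 22 × 0.01 = 1.22.
- SE = 6 × √[(1.22/23) × (1/16 + 1/16)] = 0.489.
- Noncentral t, 30 df, noncentrality 2/0.489 = 4.09: power 93.4%, in line with the SAP's figure of over 90%. The same method reproduces all 12 sample sizes in SAP Table 1.

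**2. Assumptions not in the documents.** Lifetime history in 30% of women (range 20-40%). A 24-week QIDS difference β of 1-2 points by history, given the other covariates. SD 5-6 (the SAP gives about 6; 5 allows for baseline adjustment). ICC of history 0.01 (range to 0.05).

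**3. Chance imbalance, home-visitor-led v control.** With 6 × 23 = 138 control women and 15 × 23 = 345 home-visitor-led women:
- 95% limit = 1.96 × √[0.3 × 0.7 × (1/138 + 1/345) × 1.22] = 1.96 × 0.051 = 0.100, or 10 percentage points.
- Shift in the estimate = β × 0.100 = 0.10 to 0.20 points.
- The SAP's power section counts 16 home-visitor sites (368 women) where its randomization section counts 15. With 16 the limit is 0.099.
- Over 20-40% prevalence at ICC 0.01, the limit is 0.087 to 0.107 (shift 0.09 to 0.21). At ICC 0.05 and 40% prevalence it is 0.140 (shift 0.14 to 0.28).

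**4. Chance imbalance between the two intervention arms.** At 16 v 16 sites: 1.96 × √[0.21 × 1.22 × 2/368] = 0.073, a shift of 0.07 to 0.15 points.

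**5. Precision.** Variance explained = β² × p(1 − p)/SD².
- Low end: 1 × 0.21/36 = 0.006. SE falls by 1 − √(1 − 0.006) = 0.3%.
- High end: 4 × 0.21/25 = 0.034. SE falls by 1 − √(1 − 0.034) = 1.7%.
- At 40% prevalence the high end is 4 × 0.24/25 = 0.038, a fall of 1.9%.

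**6. Steps 3 and 5 are one cost.** The unadjusted home-visitor-led v control SE is 6 × √[1.22 × (1/138 + 1/345)] = 0.67. With β = 2, chance imbalance contributes an SD of 2 × 0.051 = 0.102. Its share of the variance is (0.102/0.67)² = 0.023, which equals the variance explained at SD 6 (0.84/36 = 0.023). The imbalance is already inside the standard error.

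**7. Effect on power.** Replacing SD 6 by 6√(1 − R²) in step 1, for an assumed partial R² of 1%, 2% and 5%, gives non-inferiority power of 93.7%, 93.9% and 94.6%. Sites needing 20 women for 90% power at ICC 0.01 would need 20, 20 and 19.

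**The case against.** The case for leaving the plan alone has real force.

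- **There is no contradiction.** The SAP explains why its listed covariates are in; it does not promise to include every prognostic variable. The protocol uses the risk-factor list to justify broad eligibility, not to choose covariates. That evidence concerns developing postpartum depression, whereas the primary outcome is a symptom score adjusted for its own baseline. This stands, so the point is an improvement and not an error.
- **Depression history is partly covered.** A reader might infer that current MDE status is the only depression-related covariate. It is not: baseline QIDS-SR16, counseling and medication are there too. They overlap with history, so the independent contribution may lie below the range shown.
- **The choice could look selective.** Social support and partner relationship are on the same risk-factor list, are measured at baseline, and are also omitted. That is so. Lifetime MDE is simply the clearest case, because half of its instrument is already in the model.
- **List order is not rank.** History comes first in a lettered list, but the protocol does not say that it is the strongest factor.
- **MDE incidence.** A reader might infer a larger precision loss there, because the risk-factor evidence concerns onset. Nothing here computes one. In a logistic model, adding a prognostic covariate changes the conditional odds ratio and need not shrink its standard error.
- **Systematic imbalance.** Sites refer women after allocation, eight programs dropped out, and the analysis set requires 24-week data, so a reader might infer that history differs between arms for reasons other than chance. The documents do not show that it does. A baseline row would let readers check.

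**Conclusion.** The point holds as a minor improvement. A prognostic variable that the protocol itself highlights, and collects for analysis, is missing from the pre-specified adjustment set without explanation, and the covariates included replace it only in part.

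It would be wrong to infer that the primary comparison is biased or its test invalid: leaving out a baseline covariate does neither under randomization. The gain is at most about 2% in the standard error. Equivalently, it is protection against a 0.1-0.2 point shift at the 95% limit for home-visitor-led v control, against a five-point target difference and a two-point margin. Non-inferiority power would rise by roughly 0.2 to 1.2 percentage points at a partial R² of 1-5%. These sizes rest on assumed prevalence, effect and ICC, which the documents do not supply.

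**What to change.** Before database lock:

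1. Add lifetime MDE before baseline (yes/no) to the pre-specified covariates of the adjusted QIDS-SR16 and MDE models, alongside the current-MDE indicator, or state why it is left out.
2. Write down the MMS scoring rule. The SAP scores only the two-week window, so the rule should also say how to classify a woman whose only episode is the one present at baseline.
3. Report lifetime MDE by arm in the baseline table. The shells are non-binding, so this is one added row.
4. Specify missing-data handling for this variable. SAP, Analytic Dataset, fills missing baseline values from a participant's follow-up. For lifetime MDE that could bring in episodes after randomization. A missing indicator, or multiple imputation from baseline data only, avoids this.

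The cost is one degree of freedom, a short scoring rule and an exception to the imputation rule. The adjusted odds ratio for MDE would be conditional on one more factor, which the text should say. Timing matters: the SAP allows documented updates and bars formal analysis before lock, whereas covariate analyses that are not pre-specified will be labelled post hoc.

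### The adjusted primary model omits baseline social support, which the protocol names among the strongest risk factors and already collects; adding it would be a small gain in precision and in protection against chance imbalance

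*SAP*

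**What the plan says.** The SAP (Demographics and Baseline Assessments) lists the adjustment covariates: minority status, first-time motherhood, MDE status at baseline, language, education, and two indicators of mental health service use (counseling and medication). Its reason is that "Primary analyses will adjust for these covariates as we anticipate they will influence outcome". Under Statistical Methods the primary linear mixed model has "independent fixed effect variables of baseline QIDS-SR16, study arm (three-level factor), and the baseline covariates listed above", with a random site effect. Adjusted and unadjusted estimates are both to be reported.

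Protocol section 3.0 lists six factors that meta-analyses associate most strongly with postpartum depression. The first two are a history of depression and elevated symptoms in pregnancy; the others are "c) poor social support, d) stressful life events, e) poor marital relationship, and f) low socioeconomic status". Protocol Table 4 (section 4.0) schedules the "MOS Social Support Survey" at baseline, 12 weeks and 24 weeks.

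In the SAP, social support is a secondary outcome only, split at a score of 4 because it is highly skewed. It is not a primary-model covariate, one of the three site-level variables constrained at randomization, or an Aim 3 effect modifier.

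**The concern.** The SAP chooses covariates for their expected influence on outcome. By that rule a factor the protocol ranks among the strongest, already measured at baseline, is a natural candidate, and its absence is unexplained.

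The arm comparison rests on 37 sites: 16 MH, 15 HV and six control. The randomization constrained percent non-White clients, client volume and population density, so social support can differ between arms by chance, most easily in the contrast with six control sites. Such a difference would move the estimate in the one allocation that was realized, to the extent that support predicts 24-week QIDS-SR16 beyond the planned covariates.

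Pre-specification matters too. SAP table shell 2 will show baseline social support by arm. If it is imbalanced, the plan has no adjustment ready, and one added then would be data-driven.

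**Working it through.** **Inputs from the SAP.** SD 6; non-inferiority margin 2; superiority difference 5; significance level 5%/3 (written as 1.7%); 23 women analyzed per site; outcome ICC 0.01; 15 HV, 16 MH and 6 control sites.

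**Assumed, not in the documents.** Partial correlation r of baseline social support with 24-week QIDS-SR16, after the planned covariates: 0.10 to 0.25. Site ICC of social support: 0.05, with 0.01 to 0.10 as a range.

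**1. Reproduce the plan's figure.** Use a cluster-level two-sample t-test with k1 + k2 − 2 degrees of freedom and

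SE = 6 × √[(1 + (m − 1) × ICC)/m × (1/k1 + 1/k2)].

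At two-sided 0.017 and a difference of 2, the per-site numbers for 90% power are 17/20/25/33/49/97 with 16 sites per arm and 19/22/28/38/62/168 with 15. These are all 12 analyzed-per-site entries of SAP Table 1. At 0.05/3, power for 16 v 16 sites, 23 per site and ICC 0.01 is 93.3%, consistent with the stated figure of over 90%.

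**2. Precision and power with the covariate added.** For 15 v 16 sites, SE = 6 × √[(1.22/23) × (1/15 + 1/16)] = 0.497. Replace SD 6 by 6 × √(1 − r²).

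| r | SD | SE factor | Power, HV v MH |
|---|---|---|---|
| none | 6.00 | 1.000 | 92.4% |
| 0.10 | 5.97 | 0.995 | 92.6% |
| 0.25 | 5.81 | 0.968 | 94.0% |

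Superiority power for five points (15 HV v 6 control sites) exceeds 99% with or without the covariate.

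**3. Chance imbalance.** The SD of the standardized baseline difference is √[(1 + 22 × ICC)/23 × (1/k1 + 1/k2)]. At covariate ICC 0.05:

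- HV v MH: √[(2.10/23) × (1/15 + 1/16)] = 0.109
- HV v control: √[(2.10/23) × (1/15 + 1/6)] = 0.146

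The shift in the estimate is imbalance × r × 6. At 1.96 SD:

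- HV v MH: 1.96 × 0.109 × 6 × (0.10 to 0.25) = 0.13 to 0.32 points
- HV v control: 1.96 × 0.146 × 6 × (0.10 to 0.25) = 0.17 to 0.43 points

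With covariate ICC 0.01 to 0.10 (imbalance SD 0.083 to 0.134 and 0.111 to 0.180), the same formula gives 0.10 to 0.39 and 0.13 to 0.53. Using the full SD of 6 takes no credit for the planned covariates, so for a given r the shifts lean high.

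**The case against.** The case for leaving the model alone is substantial.

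- **Most of the prognostic information is already there.** Baseline QIDS-SR16 and MDE status measure elevated symptoms in pregnancy directly, and education stands in part for socioeconomic status. Only the increment is lost, and the documents do not quantify it. This stands, and it is why the gain is small.
- **The risk-factor list serves another purpose.** Protocol section 3.0 uses it to justify not screening on symptoms. It adds that "nearly all HV clients exhibit one of these risk factors, with most clients exhibiting multiple risk factors" and that program eligibility mirrors these factors, low social support among them. A restricted range could weaken the correlation. This too stands, and it argues for the lower end of the assumed range.
- **A short pre-specified list is accepted practice.** The SAP's sentence explains the covariates it lists; it does not promise every prognostic variable. So no rule or stated figure is broken.
- **Social support is highly skewed.** That bears on its use as an outcome. A covariate need not be normally distributed.
- **Missing baselines.** The SAP (Analytic Dataset) would fill a missing baseline value from the participant's follow-up. For a score the course may change, that would put a post-intervention value among the covariates. The objection is sound, and the fix has to deal with it.

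Three stronger readings are tempting. First, a reader might infer that the protocol measures a second named factor, stressful life events, at baseline and omits that too. It does not: the "4-item Perceived Stress Scale" measures perceived stress, a different construct, and Table 4 shows no life-events instrument. Second, a reader might set the shifts against the room left under the margin of 2, or consider an HV v MH imbalance as large as 0.3 SD. An imbalance of that size is 0.3/0.109 = about 2.8 chance SDs. The SE of 0.497 also uses the full SD of 6, so chance imbalance in unmodelled covariates is already inside the interval. Third, because women are recruited after sites are allocated, a reader might infer a systematic difference in social support. The documents describe that sequence but do not show that case mix differs by arm.

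**Conclusion.** The point holds as a modest, optional improvement. By the SAP's own reason for choosing covariates, baseline social support belongs in the adjusted primary model, and its omission is unexplained. Leaving it out does not bias the randomized comparison in expectation and contradicts no figure in the plan.

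Under the assumed r, the standard error falls by about 0.5% to 3% and non-inferiority power gains between 0.2 and 1.6 percentage points. The adjustment would guard against chance shifts of up to about 0.3 points for HV v MH and 0.4 for HV v control at the 1.96-SD extreme with covariate ICC 0.05. No conclusion about the adequacy of the sample size changes. The size rests on the assumed correlation and covariate ICC; the omission itself can be read directly from the documents.

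**What to change.** Before database lock, add the baseline MOS social support score, as a continuous variable, to the covariate list of the adjusted primary model and to the imputation model. If the sponsor prefers the present list, state why.

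Two further baseline measures may be added on the same ground. One is the 4-item Perceived Stress Scale, described as a related prognostic measure and not as a measure of stressful life events. The other is lifetime MDE from the Maternal Mood Screener ("Current & Lifetime Major Depressive Episode" in Table 4), since a history of depression heads the protocol's list.

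Exempt these scores from the rule that fills a missing baseline from follow-up, because follow-up values may be affected by the intervention. Use imputation from baseline data only, or multiple imputation.

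The cost is a short SAP amendment, one degree of freedom per added score, and a stated rule for missing baseline scores. No new data are needed.
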